Participants for this protocol will be accrued from a population of males and females 18 years of age and older who have a confirmed or suspected bladder tumor which will be treated with TURBT (or planned cystoscopy with biopsies) or cystectomy (total or partial). Eligible participants will be randomly assigned to either 600 mg erlotinib PO or matching placebo once weekly for 3 doses preceding their scheduled bladder surgery. The study will be terminated when all participants have completed study dosing, their scheduled surgical treatment, and a 7-14 day post-surgery follow-up period.

There is no run-in period specified for this protocol. Potential study participants will be identified from the population of patients being evaluated and treated for bladder tumors at each of the participating institutions. After being presented with information about the protocol, patients interested in participating will be scheduled for a screening/baseline study visit. After completion of the informed consent process, the following assessments/procedures will be conducted:

Screening/Baseline visit (within 30 days of first dose of study agent):

- eligibility assessment
- medical/surgical history and baseline symptoms
- physical exam/vital signs (including performance status assessment)
- clinical safety labs (including pregnancy testing for females of childbearing potential)
- plasma pharmacokinetics
- request for randomization
- International Prostate Symptom Score (I-PSS)

Study agent and topical ointment (topical clindamycin, topical hydrocortisone) dispensing: (within 30 days of baseline assessments) either in clinic or study agent will be mailed to the participant via overnight courier with a phone contact prior to dosing. Ointment instructions will be included (See Appendix B).

- study agent dosing instructions
- ointment instructions
- concomitant medication review and adverse event assessment

Pre Day 8 Phone contact (approximately 24-72 hours prior to Day 8 Visit):

- instruct participant on dose and time of Day 8 study drug administration

Day 8 Visit*:

- physical exam/vital signs (including complete assessment of any rash per CTCAE criteria)
- clinical safety labs
- plasma pharmacokinetics
- Day 8 Study dosing after plasma pharmacokinetics
- concomitant medication review, compliance and adverse event assessment

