*The day 8 clinic visit will be optional; if the participant opts out then a post day 8 phone contact (within 48 hours of taking dose) will be required for a concomitant medication review, compliance and adverse event assessment.

Pre-Surgery reminder Phone contact (approximately 24-72 hours prior to Surgery):

- instruct participant on dose and time of pre-surgical study drug administration

Surgery visit: (Day 15-16):

- physical exam/vital signs
- clinical safety labs
- plasma pharmacokinetics
- concomitant medication review, compliance and adverse event assessment
- International Prostate Symptom Score (I-PSS)
- collection of paraffin-embedded blocks or slides after standard pathology processing

Post-Surgery phone contact (7-14 days post-surgery):

- concomitant medication review and adverse event assessment

Duration of study participation will range from 29-56 days depending upon how long before the day 1 study agent dosing occurs after the screening/baseline assessments.

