5.2 Study Agent Administration

The study agent (erlotinib or placebo) will be dispensed by an investigational pharmacist or appropriate study staff at the participating organization (PO) and then self-administered by the participant at home. A single bottle containing 16 tablets of study agent will be dispensed. If the participant is unable to return to the institution to pick up their study agent, the agent will be mailed to them via courier.

The study agent must be taken on an empty stomach (at least two hours after last eating). After taking their dose of study agent the participant must wait an hour before eating anything.

On Day 1, the participant will take one dose, 600 mg erlotinib or placebo in the form of four 150 mg erlotinib or matching placebo tablets by mouth in the evening (unless otherwise directed) on an empty stomach. All 4 tablets comprising a single dose of study agent will be taken together at the same time.

On Day 8, the participant will take their second dose of study agent (600 mg erlotinib or placebo in the form of four 150 mg erlotinib or matching placebo tablets) on an empty stomach as instructed either in the clinic following the collection of blood samples for pharmacokinetics or at home. Prior to the Day 8 Optional Visit/Mandatory Safety Assessment Phone call, the participant will receive a reminder phone contact instructing the participant when to take the Day 8 dose.

On Day 15 the participant will take their third dose of study agent approximately 9-18 hours before their scheduled surgery (600 mg erlotinib or placebo in the form of four 150 mg erlotinib or matching placebo tablets). The participant will receive a reminder phone contact prior to their final study dosing day instructing them when to take this final dose.

If surgery is delayed beyond the 16th day but less than the 23rd day, delay administration of the third dose until approximately 9-18 hours prior to the surgery. If surgery is delayed to day 23 through day 28, administer the third dose at day 15, and the fourth dose approximately 9-18 hours before surgery. If

surgery is delayed beyond day 28 (four weekly study drug doses), the patient will be considered not evaluable for the primary endpoint.

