5.6 Dose Modification

Study drug will be dose reduced (by 50%) from 4 tablets to 2 tablets for any of the following events:

- A grade 1 rash or diarrhea that the study subject finds unacceptable and desires the 50% dose reduction.
- A grade 2 skin toxicity
- A grade 2 diarrhea that does not respond to Imodium
- Any toxicity or adverse event \geq grade 3
- MD discretion for side effects assessed as at least possibly related to the study drug and for which the study subject finds unacceptable and desires the 50% dose reduction

Subjects that meet the above dose modification criteria even after a dose reduction will not receive any further doses. At the first report of grade 1 or 2 skin toxicity, subjects should be instructed on using the dispensed topical ointments (1% Clindamycin, 1% hydrocortisone): apply twice daily (not at the same time) each ointment to the affected area only. Subjects who report grade 1 or 2 diarrhea likely to be attributable to study drug should be instructed to use loperamide (Imodium) 2 mg after each loose stool. Provide participants with a copy of Appendix B.

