7. Day 8 clinic visit will be optional; if participant opts out a mandatory phone call to review safety assessments will be required within 48 hours of taking the Day 8 dose.

All participants who sign a consent form will be assigned a registration number. The consent form must be signed before any research procedures may be performed. The assigned registration number will be tracked using the registration log provided by the CLO. Registered participants need to be entered into the OnCore database.

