7.3 Evaluation During Study Intervention

Special Drug Dosing Procedures

The participant must be instructed to take the medication in the evening on an empty stomach (no food within two hours before ingestion and within one hour post-ingestion) on day 1, 8 and 15 with the scheduled surgery on day 16. To ensure compliance, participants will be instructed verbally and in writing to take 4 tablets from their dispensed bottle on the scheduled evenings (study days 1, 8, and 15).

Drug Dispensing

Study agent will be shipped to the PO on a per participant basis. The request to ship study agent will be sent by the CLO once a request for participant randomization has been received from the site and eligibility has been verified by the CLO (refer to section 6.8). The bottle of study agent shipped to the PO will be identified with the randomization number assigned to the participant. When the participant's study agent arrives at the PO it may be dispensed to the participant. If the institution requires a prescription for investigational agents, the site coordinator or pharmacy staff must clearly document that all prescription procedures were followed before drug was dispensed to the participant.

Reminder Phone Contact Before Day 8 Visit

Approximately twenty four to seventy two hours before the Day 8 Visit, the participant will be contacted by phone and reminded about their Day 8 appointment time. The participant will also be reminded about study dose (timing, any dose modifications, how to take it, etc.).

Day 8 Visit*

Participants will be seen and evaluated by research staff on day 8 prior to ingesting their day 8 study dose. The evaluation includes vital signs, review any adverse events that took place including an assessment of toxicities (especially skin toxicity and diarrhea) and concomitant medications. Blood for safety labs and pharmacokinetics will be obtained. The coordinator should collect and calculate study drug compliance. If dose modifying toxicity (as described above) has occurred, study staff will instruct the participant on their modified study dose (3 tablets) for day 8 and 15. After completion of this assessment the day 8 study dose will be taken as instructed.

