*Day 8 clinic visit is optional. If participant decides to opt out; a Day 8 phone call to evaluate safety assessments will be required. This phone call should occur after the day 8 dose is taken and within 48 hours of the dosing. The call should include an evaluation of toxicities, a review of concomitant medications and compliance.

Reminder Phone Contact Before Surgery

Approximately twenty four to seventy two hours before surgery or cystoscopy with biopsy, the participant will be contacted by phone and reminded about their last study dose (timing, any dose modifications, how to take it, etc.) and returning any leftover study medication and study medication bottles to the research

staff. The participant will also be reminded about the appointment(s) on the day of surgery with study staff.

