APPENDIX B

Information on Erlotinib (Study Drug)

Erlotinib
(Tarceva)

Description

Erlotinib is a medication used in the treatment of some cancers. This study is being done to determine the potential cancer prevention effects in bladder tissue when erlotinib is taken once a week, and to determine how well people tolerate taking erlotinib once a week. Erlotinib needs to be taken on an empty stomach, which means taking it at least 2 hours after you last ate something one hour before you next eat something.

How It Is Given

This medicine is a pill that you swallow.

When to call us: We would like to know if you experience any rash or diarrhea that continues for over 24 hours. We would also like to know if you experience any unexplained, persistent cough, fever, or shortness of breath immediately.

Common Side Effects When Taken Daily:

COMMON, SOME MAY BE SERIOUS In 100 people receiving erlotinib, more than 20 may have:

• Rash• Diarrhea• Loss of appetite• Tiredness or fatigue• Shortness of breath• Cough• Nausea• Infection• Vomiting

OCCASIONAL, SOME MAY BE SERIOUS

In 100 people receiving erlotinib, from 4 to 20 may have:

- Sores in mouth
- Itching
- Acne
- Dry skin
- Weight loss
- Irritation (redness, swelling, warmth, and pain) or infection of the skin around fingernails or toenails
- Eye infection/pink eye
- Dry eyes
- Stomach pain or pain in the abdomen (belly)
- Red bumps on the skin that are red, sore, and possibly infected

POSSIBLE, SOME MAY BE SERIOUS

The frequency of some individual side effects for people receiving erlotinib has not yet been determined:

- Shoulder pain
- Change in urine color
- Indigestion
- Gas in the belly, burping
- Irritability (easily annoyed or made angry)
- Swelling of the face, hands, feet or ankles
- Runny nose
- Dizziness
- Headache
- Blood clot in the lung which may cause pain, shortness of breath
- Stroke (Stoppage of blood flow to your brain which may cause paralysis, weakness, headache)
- Death or injury to unborn baby
- Because of the potential harm to the infant, women should be advised against breast-feeding while receiving erlotinib therapy

RARE, SOME MAY BE SERIOUS

In 100 people receiving erlotinib, 3 or fewer may have:

Although very rare, some of the side effects listed below can cause death

- Abnormal laboratory result which may indicate liver damage
- Liver damage
- Kidney damage which may cause swelling, may require dialysis

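### Participants who skip the Day 8 visit have no scheduled toxicity review before dose 2, so the mandatory dose reduction depends on self-report

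*Combined protocol and SAP*

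**What the plan says.** Section 5.6 sets the rule: "Study drug will be dose reduced (by 50%) from 4 tablets to 2 tablets for any of the following events". Three of its five triggers apply whatever the participant prefers: grade 2 skin toxicity, grade 2 diarrhea not responding to loperamide, and any event of grade 3 or higher. Section 13.4 also describes the reduction to 300 mg for grade 2 rash or diarrhea as required.

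For those who attend on Day 8, Section 7.3 puts the review first: "Participants will be seen and evaluated by research staff on day 8 prior to ingesting their day 8 study dose". Any modified dose is given to the participant at that point.

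The visit is optional. For those who decline it, three places time the substitute call by reference to a dose already taken:

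- Section 7.3: "This phone call should occur after the day 8 dose is taken and within 48 hours of the dosing".
- Section 7.1, note 7: "if participant opts out a mandatory phone call to review safety assessments will be required within 48 hours of taking the Day 8 dose".
- Section 3: "if the participant opts out then a post day 8 phone contact (within 48 hours of taking dose) will be required".

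The scheduled contact before dose 2 is the reminder call 24-72 hours ahead of Day 8. Section 3 gives its purpose as "instruct participant on dose and time of Day 8 study drug administration". Section 5.2 says "the participant will receive a reminder phone contact instructing the participant when to take the Day 8 dose". Section 7.3 adds that the call reminds the participant of dose modifications. The Section 7.1 schedule marks that column for the dose reminder and has no Adverse Events mark there.

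**The concern.** A dose-reduction rule works only if someone learns of the toxicity before the next dose. Attendees are asked. Opt-outs are asked only after dose 2 has been swallowed. Before then the rule depends on the participant ringing the site.

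An opt-out who reacts to dose 1 at a Section 5.6 level and stays silent would take a second full dose, twice what the protocol requires. An attendee with the same reaction would be asked about it first. The plan gives no reason for the difference. The trial is in a prevention setting, ranks tolerance first among its secondary objectives, and expects that a number of participants may need a reduction (Sections 3, 13.1 and 13.4).

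**Working it through.** The point is procedural and the plan states no figure to reproduce. The check is to list every scheduled contact between dose 1 and dose 2 for the two kinds of participant.

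| Step | Attends Day 8 | Opts out of Day 8 |
|---|---|---|
| Reminder call, 24-72 h before Day 8 | Dose and timing; no Adverse Events mark | Same |
| Day 8, before the dose | Toxicity review, vital signs, safety labs | None |
| Dose 2 | Taken after the review, reduced if needed | Taken at home |
| After dose 2 | No separate safety call | Safety call within 48 h |
| **Scheduled toxicity reviews between doses 1 and 2** | **1** | **0** |

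Two entries could be thought to fill the gap, and neither does. The adverse event assessment that Section 3 lists with dispensing comes before dose 1. The mention of dose modifications in Section 7.3's account of the reminder call passes on a decision already made; it does not tell staff to find out whether one is needed. The post-dose call comes before dose 3, so dose 3 is covered.

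**Size, under stated assumptions.** The documents give 30 erlotinib participants. They give neither the opt-out rate nor the rate of qualifying events at 600 mg weekly, so both are assumed.

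Expected number reaching dose 2 unreviewed = 30 × opt-out rate × rate of qualifying events before Day 8.

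- Low: 30 × 0.10 × 0.05 = 0.15
- Middle: 30 × 0.50 × 0.10 = 1.5
- High: 30 × 0.75 × 1/6 = 3.75

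The upper event rate is the 17% grade 2 rash rate that Section 2.2 reports at 1200 or 1600 mg weekly, which is 2 to 2.7 times this trial's dose (1200/600 and 1600/600). It is consistent with 1 of 6 patients, for which the exact 95% interval is 0.4% to 64%.

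A second calculation for grade 2 rash alone allows for onset after Day 8: 30 × rash rate × share with onset by Day 8 × opt-out rate.

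- Central: 30 × 0.17 × 0.50 × 0.50 = 1.3
- Low: 30 × 0.10 × 0.25 × 0.25 = 0.19
- High: 30 × 0.42 × 0.75 × 1.00 = 9.45

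The 42% is the rate reported at 2000 mg weekly. The 10%, the onset shares and the opt-out rates are assumptions. Neither calculation allows for self-report, which would lower every figure.

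**The case against.** The strongest reply is that the plan does provide for reporting. Appendix B tells participants "We would like to know if you experience any rash or diarrhea that continues for over 24 hours". Section 5.2.1 asks for a call if skin lesions persist or worsen, or at 3-4 watery stools a day. For rash and diarrhea these prompts set no toxicity grade, so they can operate below the mandatory thresholds. Section 7.2 provides a calendar for side effects and encourages contact with staff. Section 11.1.1 requires all adverse events after baseline to be recorded, so toxicity volunteered on the reminder call would count. Two of the five Section 5.6 triggers turn on the participant wanting a reduction, so they need no staff review.

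The likely harm is also modest. Section 2.2 reports that weekly doses up to 1600 mg did not define a maximum tolerable dose, that severe skin disorders appeared at 1400 and 1600 mg, that rash tended to improve with continued weekly dosing, and that loperamide controlled diarrhea well. In the daily-dosing lung cancer study in Section 6.2, median rash onset was 8 days, so many rashes may follow dose 2. A call after dose 2 can also pick up diarrhea from that dose, and the optional visit reduces burden.

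All of this is fair, and it bears on how many people are affected and how badly. It does not supply the missing review. Self-report is also an incomplete substitute:

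- Under Section 5.2.1, skin lesions prompt a call only after topical treatment has failed.
- Appendix B's call-in list covers rash, diarrhea, cough, fever and shortness of breath. Other grade 3 events have no prompt there.
- Safety labs are drawn at the visit opt-outs skip, so they cannot report a laboratory event.
- Section 7.3 has participants instructed, verbally and in writing, to take four tablets on Days 1, 8 and 15. Silence means the full dose.

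**Conclusion.** The concern holds. Between doses 1 and 2 the plan schedules one toxicity review for attendees and none for opt-outs, and three sections agree on the post-dose timing, so this is not a slip of wording in one place. The consequence is confined to dose 2: 600 mg taken where 300 mg is required.

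The number affected cannot be estimated from the documents. About 0.2 to 3.8 of the 30 erlotinib participants follows from assumed opt-out rates of 10-75% and event rates of 5-17%, with no self-report. The upper event rate is probably high for rash, because it comes from larger doses and some rash would start after Day 8. At the low end nobody would be expected to be affected. The case for changing the plan rests on a mandatory safety rule having no scheduled trigger at this dose, and on how little the remedy costs.

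**What to change.** Add a toxicity review against the Section 5.6 criteria to the reminder call already made to every participant 24-72 hours before Day 8, and apply any required reduction to the Day 8 dose on that call. Amend Sections 3, 5.2 and 7.3 accordingly, and place an Adverse Events mark in that column of the Section 7.1 schedule. Keep the optional visit and the post-dose call. The same amendment should settle the reduced dose, which Section 7.3 gives as three tablets and Section 5.6 as two.

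The cost is a few minutes per call, one CRF entry and a short amendment, with no extra contact. The change will not catch laboratory events or rash that begins after the call. Section 2.2 reports that diarrhea on weekly dosing generally began within 24-48 hours, so diarrhea from dose 1 should usually have appeared by then.

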4.4 Recruitment and Retention Plan

In an attempt to address participant concerns about extra visits, missed work, and transportation expenses, we have minimized the number of study visits in this protocol. After the consent form is signed, all baseline/screening procedures and examinations will be done at one visit, including research blood sample collection (Urine sample collection will be collected only as pregnancy test option for women of child bearing potential). Participants found to be screen failures, will not be randomized and the research samples will be destroyed on-site. Eligible participants will have two additional study visits, one at Day 8* and one on the day of their surgery.

*The Day 8 clinic visit is optional; a Day 8 phone contact will be required if clinic visit doesn't occur

Study brochures, posters, protocol fast fact sheets, pocket cards, and other recruitment materials will be developed at the CLO (Consortium Lead Organization, University of Wisconsin) and made available to the participating sites for use or modification. The CLO will coordinate with the other sites to develop comprehensive site-specific recruitment plans.

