7. CLINICAL EVALUATIONS AND PROCEDURES

7.1 Schedule of Events

Evaluation/ Procedure	Pre-Study Evaluation/ Baseline (≤30 days)	Randomize / Dispense Study Agent	Phone Contact (24-72 hours Prior to Day 8 Visit)	Day 8 Visit ⁷	Pre-surgery phone contact (24- 72 hours prior to surgery)	Surgery Visit (day 15-16)	Post-surgery Phone Contact (7- 14 days after surgery)
Informed Consent	X						
Assess Eligibility	X						
Medical History	X						
Physical Exam	X ²			X ²		X ²	
Baseline Symptoms	X						
Vital signs (temp, pulse, BP, Ht and Wt)	X			X		X	
Hgb, Hct, WBC, Plt	X			X		X	
Na, K, CO ₂ , Cl	X			X		X	
BUN,Creat	X			X		X	
AST, ALT, Alk Phos	X			X		X	
T Bili	X			X		X	
Urine or Serum Pregnancy Test	X						
Blood for PK	X			X		X	
Tissue Blocks/slides						X	
Concomitant Meds	X			X ⁷		X	X
Dose of study agent		X ¹		X ³	X ^{4,5}		
Dose reminder call			X		X		
Dispense 1% clindamycin & 1% hydrocortisone		X ⁶					
I-PSS (men only)	X					X	
Compliance				X ⁷		X	
Adverse Events				X ⁷		X	X

- The date of the Day 1 dose equals the date of the surgery minus 15 days. For example, if the surgery was on the 23rd of the month, 23-15= 8, therefore the participant would take their 1st dose of study agent on the 8th of the month.
- Physical exam should include evaluation for rash. If a rash is noted, document the extent of the rash per CTCAE grading criteria
- The Day 8 dose of study agent should be taken during the clinic visit after the pharmacokinetic blood draw is completed or at home as instructed by study staff.
- The pre-surgical dose of study agent should be taken in the evening prior to the day of surgery and within approximately 9-18 hours of the time of the pre-surgery pharmacokinetic blood draw.
- If surgery is delayed beyond the 16th day but less than the 23rd day, delay administration of the third dose until the evening prior to the day of surgery. If surgery is delayed to day 23 through day 28, administer the third dose at day 15 and the fourth dose in the evening prior to day of scheduled surgery. If surgery is delayed beyond day 28 (four weekly study drug doses), the patient will be considered not evaluable for the primary endpoint. A reminder phone contact should be made 72 – 24 hours prior to the day of the re-scheduled surgery.

6. Dispense to all study participants when dispensing medication per NCI requirements. Instruct participant to use these agents for skin toxicities.

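### The protocol schedules no toxicity review between dose 2 and the final dose for Day 8 clinic attendees, and none before dose 2 for opt-outs, so section 5.6 depends on self-report in those windows

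*Combined protocol and SAP*

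**What the plan says.** **Attendees.** Section 7.3 places the Day 8 review before dose 2: "Participants will be seen and evaluated by research staff on day 8 prior to ingesting their day 8 study dose". If toxicity calls for a change, "study staff will instruct the participant on their modified study dose (3 tablets) for day 8 and 15".

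**Opt-outs.** The Day 8 visit is optional. For those who decline it, section 7.3 requires a call and fixes its timing: "This phone call should occur after the day 8 dose is taken and within 48 hours of the dosing". Footnote 7 of the Schedule of Events (7.1) agrees: "if participant opts out a mandatory phone call to review safety assessments will be required within 48 hours of taking the Day 8 dose". So does section 4.4: "a Day 8 phone contact will be required if clinic visit doesn't occur".

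**The pre-surgery call.** Everyone is called 24-72 hours before surgery. Under 7.3 the participant is "contacted by phone and reminded about their last study dose (timing, any dose modifications, how to take it, etc". Section 3 lists one item for this call, instruction on the dose and its time. In the 7.1 table the Adverse Events row is marked at Day 8, the surgery visit and the post-surgery call, but not in this column.

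**Delayed surgery.** Footnote 5 of 7.1 adds a fourth dose: "If surgery is delayed to day 23 through day 28, administer the third dose at day 15 and the fourth dose in the evening" before surgery. It also calls for a reminder contact 72-24 hours before the new surgery date.

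**Dose rules.** Section 5.6 cuts the dose from four tablets to two on listed triggers and adds a stop rule: "Subjects that meet the above dose modification criteria even after a dose reduction will not receive any further doses".

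**The concern.** A review held before dose 2 cannot detect a reaction to dose 2. Section 2.2 reports that diarrhea on weekly erlotinib generally came 24-48 hours after a dose. After a Day 8 dose that is Day 9-10, when the attendee review is already over. For someone reduced on Day 8, the stop rule in 5.6 has no scheduled point at which it could be triggered before the next dose.

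The pre-surgery call has to pass on any dose modification, yet no scheduled step tells staff whether one is needed because of dose 2. A site that follows the schedule exactly can therefore give the final dose unchanged to a participant who already meets a reduce or stop criterion.

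Opt-outs have a similar gap one dose earlier. Their first scheduled toxicity review comes after dose 2, so a reaction to dose 1 need not be known when dose 2 is taken. What is at stake is patient safety and uniform use of 5.6 across six sites.

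**Working it through.** The plan has no figure of its own on this point to reproduce. The check lists the scheduled contacts against the doses, then prices a missed modification.

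**1. Attendees: days from the Day 8 review (before dose 2).** Dose 3 falls on the day before surgery for surgery on days 16-22, and on Day 15 for surgery on days 23-28. Dose 4 falls on the day before surgery. Days to a dose = dose day - 8; days to the next review = surgery day - 8.

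| Surgery day | Days to dose 3 | Days to dose 4 | Days to next adverse event review | Toxicity reviews or safety labs after dose 2 and before the final dose |
|---|---|---|---|---|
| 16 | 15 - 8 = 7 | none | 8 | 0 |
| 17-22 | 8-13 | none | 9-14 | 0 |
| 23-28 | 7 | 14-19 | 15-20 | 0 |

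**2. Opt-outs.**
- Dose 1 to dose 2: 0 scheduled toxicity reviews. The pre-Day 8 call, 24-72 hours before Day 8, is a dose reminder.
- After dose 2: one review, on Day 8-10. For a Day 15 dose that leaves 15 - 10 = 5 to 15 - 8 = 7 days with no further review.

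**3. Would the existing calls come at a useful time?**
- Surgery on day 16: the call falls on Day 13-15. Against expected diarrhea on Day 9-10, that is 13 - 10 = 3 to 15 - 9 = 6 days after onset.
- The final dose is 9-18 hours before surgery, so the call precedes it by 24 - 18 = 6 to 72 - 9 = 63 hours.
- Pre-Day 8 call: Day 5-7. Diarrhea 24-48 hours after a Day 1 dose is Day 2-3, so the call is 5 - 3 = 2 to 7 - 2 = 5 days after onset.

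Both calls come after the expected onset and before the next dose.

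**4. Drug taken beyond what 5.6 allows, erlotinib arm.** Four tablets are 600 mg; the 5.6 reduction to two tablets is 300 mg.

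| Situation | Excess |
|---|---|
| One dose: should be reduced, takes full dose | 600 - 300 = 300 mg |
| One dose: already reduced, should stop, takes reduced dose | 300 - 0 = 300 mg |
| Doses 3 and 4: criterion first met after dose 3 | 300 mg (dose 4 only) |
| Doses 3 and 4: criterion met after dose 2, no reduction made | (600 - 300) + (600 - 300) = 600 mg |
| Doses 3 and 4: reduced at dose 2, criterion met again, not stopped | (300 - 0) + (300 - 0) = 600 mg |

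**5. Dependence on the tablet count.** Section 7.3 gives the modified dose as three tablets, 3 x 150 = 450 mg, against two in 5.6. Sections 13.1 and 13.4 both state 300 mg, which supports two. If a site follows 7.3, a participant who should have stopped takes 450 mg at each remaining dose, not 300 mg.

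**The case against.** The strongest reply is that safeguards already exist. Section 5.6 binds whenever staff learn of toxicity, at a visit or not. Section 5.2.1 tells participants to call about skin lesions that continue or worsen, or 3-4 watery stools a day. Appendix B asks to hear of rash or diarrhea lasting over 24 hours. Participants keep a side-effect calendar (7.2), and two of the 5.6 triggers depend on the participant wanting a reduction. The pre-surgery call is live contact that mentions dose modifications. All of this stands and narrows the gap. It does not close it: each route relies on the participant raising the problem, and no step has staff review the calendar before the final dose.

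A second reply is that the Schema and section 5.2 can be read as requiring the Day 8 safety call of everyone. Sections 3, 4.4 and 7.3 and footnote 7 of 7.1 are more specific and limit it to opt-outs.

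A third is that the onset data come from 1200-2000 mg weekly, two to over three times this dose, and that diarrhea there was controlled well with loperamide and rash improved with continued dosing. This is fair and limits the weight of the point.

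Three stronger readings are tempting, and the documents do not support them:
- A reader might infer an excess of 900 mg, as (600 - 300) + (600 - 0), for someone who meets a criterion after dose 2 and again after dose 3. That applies the stop rule as if toxicity had recurred after a 300 mg dose 3 that was never taken. The rule applies only after a reduction.
- A reader might infer that toxicity goes unrecorded. Section 7.4 reviews events at surgery, so the data are collected, only too late to change the dose.
- A reader might infer that opt-outs are simply better protected. That is true after dose 2 and false before it.

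**Conclusion.** The concern holds as a low-cost safety improvement, not a major defect. As scheduled, attendees have no toxicity assessment between dose 2 and dose 3, or between dose 2 and dose 4 when surgery is on day 23-28. Opt-outs have none between doses 1 and 2, and none from their post-Day 8 call to the final dose.

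For an affected erlotinib participant the excess is 300 mg for one dose and at most 600 mg over doses 3 and 4. These figures assume the two-tablet reduction in 5.6 and a participant who does not make contact.

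The documents give no toxicity rate for single-agent erlotinib at 600 mg weekly and no split between attendees and opt-outs, so the number affected cannot be estimated. That it is small is a judgment, resting on the self-report instructions and on how manageable toxicity was at higher weekly doses. Sample size and the primary comparison are unaffected by the gap itself.

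**What to change.** 1. Make the 24-72 hour pre-surgery call an adverse event assessment for all participants. Add an X in that column of the Adverse Events row in 7.1 and amend sections 3 and 7.3. Staff ask about and grade rash, diarrhea and other events, 5.6 is applied, and only then is the dose instruction given. The call is already repeated before a rescheduled surgery, so it also covers dose 4.
2. Ask opt-outs the same question on the existing pre-Day 8 reminder call, before dose 2.
3. When a fourth dose is planned, make one short equivalent call before dose 3.
4. Correct the three tablets in 7.3 to two, to match 5.6.

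The 5.6 criteria stay as they are. The cost is a few minutes per call, one extra call for surgery on day 23-28, and an amendment needing DCP and IRB approval (14.3).

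Two limits should be stated. Prompting may bring a few more elective grade 1 reductions. Section 5.7.1 restricts primary-endpoint evaluability to those who take all study drug, and section 13.3 allows a margin of only 45 - 42 = 3 participants; 5.7.1 should say whether a reduced dose taken as instructed counts. And a phone call cannot detect laboratory toxicity, which can also meet the grade 3 trigger in 5.6.
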